9.14. Statistical analysis plan

Statistical analysis will be performed in accordance with the principles of intention-totreat analysis. Descriptive statistics will be used to summarize the feasibility results. According to the CONSORT guide for feasibility experiments (Eldridge et al., 016), efficacy tests are not recommended, because the study is not designed to detect differences between the types of surgery, therefore, for the clinical outcomes analyzes will focus primarily on descriptive analyzes using the mean (standard deviation) or median (interquartile range) for continuous outcomes and absolute frequencies and percentages for categorical outcomes. For the specific objective of the degree of variability of the bleeding methods, the coefficient of variation of each method within the surgical techniques will be calculated. STATA version 14.0 ® software will be used.

9.15. Interim analysis:

An interim analysis will be carried out when 10 patients have been randomized, to evaluate possible factors to improve in the execution of the study. This interim analysis will be carried out by the executing institution and the research group.

10. Data collection, patient follow-up, study monitoring and clinical outcomes:

10.1. Data collection:

A CRF ("case report form") will be designed together with the systems support staff of Fundación Valle del Lili, the clinical history will be used as the source document, from which the data of interest will be obtained to be entered into the *RED Cap*® electronic platform where the variables to be studied will be recorded and the demographic data of the participants, obstetric history (pregnancy and parity) of previous surgeries that include cesarean deliveries or uterine curettage or other gynecological surgery will be collected, gestational age at diagnosis, gestational age at delivery, and birth outcome. Prenatal complications, particularly bleeding before delivery (number of episodes and quantity, blood transfusions) will be recorded.

The type of surgical procedure, the type of anesthesia, the duration of the procedure, the

surgical details, the volume of total intra-surgical bleeding, the details of the transfusion of blood components and the surgical complications, transfer to the Intensive Care Unit (ICU), length of stay in ICU in days / hours, the WHO Near Miss criteria (Appendix 1). Postoperative complications and the total length of hospital stay will be recorded.

Information will be collected about the histopathological analysis of the surgical specimen in relation to the confirmation of the pathology and the degree of invasion described in the report.

The data collected will be stored by the executing institution and the participating institutions in the *RED Cap* \mathbb{R} electronic platform, the main researchers of each of the participating centers will be in charge of collecting the information required in the protocol, each of them will have a profile used for the electronic entry of the information.

The information collected in this study will be recorded in a way that the subjects cannot be identified at any time. Any change in the process must be reported to the institutional review board (or Institutional Review Board IRB) of the clinical research center of Fundación Valle del Lili by the study coordinator.

This database will not have specific information on substance abuse, psychiatric disorders, sexually transmitted diseases, or identifier such as name or identity document number.

Information from health records such as diagnoses, progress notes, medications used, procedures performed, laboratory findings, radiology, etc. will be stored.

This study does not contemplate the use of any device or investigational drug, no specimens or biological samples will be collected from patients for this study.

It is important to note that, in the three institutions invited to participate, the principal investigators currently carry out several research projects on PAS. Thus, the prospective collection of clinical and paraclinical variables of interest in PAS is an established habit in each of the surgeries for this disease. The three clinical leaders from each institution have successfully completed several observational projects around PAS and have scientific publications in indexed journals. Additionally, they agree to submit to the audit of each of their research groups and to centralized surveillance by the research center of the Fundación Valle del Lili, during the execution of this project.

10.2. Follow up assessments:

The study participants will be followed up to evaluate the primary and secondary outcomes and the appearance of adverse events during 4 moments:

- **10.2.1. Intraoperative**: The total intraoperative bleeding volume will be measured, type of anesthesia used, type of skin incision, type of uterine incision, FIGO PAS classification, use of interventional radiology, use of intraoperative cell saver ("cell saver"), duration of surgery, use of uterine tamponade with hydrostatic balloons, gender and weight of the newborn.
- 10.2.2. **Immediate post-operatory time**: defined as the first 48 to 72 hours after the intervention, in this period of time, the patient will be monitored in the obstetric gynecological service, where each of the secondary outcomes described will be evaluated: Maternal death, Presence of Near Miss criteria, frequency and volume of transfusion of blood components, bladder injury, ureteral injury, need for reoperation, admission to ICU, days of postoperative hospital stay, disseminated intravascular coagulation, hypovolemic shock, metabolic acidosis, urinary retention, femoral thrombosis, post-operative ileus, supra fascial hematoma.
- 10.2.3. **Medical appointment between 7 and 12 days:** The patient is clinically evaluated by outpatient consultation on-site or telemedicine with the treating physician who determines if any of the secondary outcomes described above have occurred and additionally if she has developed an infection of the surgical wound.
- 10.2.4. **Follow-up at 42 days postpartum:** the patient will be followed up by telephone when she reaches 42 days after the surgical intervention, where a general evaluation of her health will be made, and the follow-up will be terminated.

10.3.Data quality monitoring:

Both the executing institution and the institutions participating in the study will designate a person in charge of monitoring the quality of the data. In the executing institution, the person in charge will be [name], who will perform a data quality analysis of 100% of the data corresponding to the primary outcome to be evaluated and 100% for the secondary outcomes, in this analysis of quality, a review of the data entered into the system will be carried out and it will be compared with the clinical records of each institution, the process will be carried permanent and will be programed the first monitoring with each center 5 days after to first participant enrollment, the additional monitoring visits will be performed according to recruitment rate and presence of primary and secondary outcomes in participating individuals.

The two institutions invited to participate will also receive supervision from the monitor of this study at Fundación Valle de Lili, who will establish frequent communication with the coordinators of the centers in Argentina and Indonesia.

- 10.4. **Duration of the study:** Taking into account the frequency of cases of this pathology per year, it is estimated that each executing institution will attend 1 or 2 cases of PAS per month, with a total duration of 24 months.
- **10.5. Study completion**: The study is considered to end for each patient 42 days after surgery when the last moment of follow-up is performed. The feasibility study ends 42 days after the cesarean section of the last randomized patient
- 10.6. Withdrawal of informed consent: The participant or their legal representative may voluntarily withdraw their consent to participate in the study for any reason and at any time. In case of withdrawal of informed consent, the usual follow-up of the patient will continue during the post-surgical period and the follow-up appointment in 7 to 12 days. The only time of the follow-up that will not be carried out will be the telephone control at 42 days postpartum. Once the informed consent is withdrawn, no further information will be collected, the information collected until the moment of withdrawal of consent will be used in the analyzes contemplated in the study.

11. Ethical considerations

The study will be submitted to the evaluation of the local ethics committee for its approval.

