1. SYNOPSIS

Data category	Information					
Registration - Study ID	Clinical Trial.gov assigned number					
Number	NCT05013749					
Registration Date	August 18, 2021					
Principal Sponsor	Centro de Investigaciones Clínicas – Fundación Valle del Lili. Cali,					
	Colombia					
Contact for public	[contact] [name]					
consultation:						
Contact for scientific	[name]					
consultation:	[contact]					
Public title:	RCT-PAS					
Scientific Title:	Hysterectomy vs partial myometrial resection for placenta accreta					
	spectrum (PAS). A feasibility study of a randomized controlled					
	clinical experiment (RCT-PAS)					
Recruitment coordination	Fundación Valle del Lili. Cali, Colombia					
center:						
Recruitment centers:	3					
Health Condition or	Placenta Accreta Spectrum (PAS)					
Problem						
Study Type	Feasibility study of an open-label (non-blinded), randomized,					
	controlled, multicenter clinical trial.					
Primary objective	To evaluate the feasibility of the parallel experimental design,					
	willingness of eligible patients to participate, and outcome measures					
	for conducting a randomized phase III clinical trial comparing					
	partial myometrial resection with hysterectomy in patients with					
	Valle del Lili, over a 24 month period					
Spacific abjactivas	- Measure the proportion of eligible patients who agree to					
specific objectives	participate in this comparison.					
	- To measure the percentage of screening failure.					
	- Describe the confirmation of the presence or absence of placental accreta spectrum in each case					
	placental accreta spectrum in each case.					
	- To identify the degree of variability between the different methods of measuring intraoperative bleeding in each of the techniques.					

Secondary objective Study design Intervention group	To identify the characteristics of the patient's current pregnancy. To describe the clinical outcomes of interest in patients randomized to hysterectomy or partial myometrial resection. To categorize the severity of surgical complications according to the Clavien Dindo classification. Feasibility study of randomized, controlled, multicenter clinical experiment on the use of partial myometrial resection vs. hysterectomy. Patients with a confirmed diagnosis of PAD (See Appendix 2, Definition of a confirmed case of PAD) Partial myometrial resection					

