Statistical analysis	It will be performed according to the principles of intention-to-treat analysis. Descriptive statistics will be used to summarize the feasibility results. According to the CONSORT guidelines for feasibility experiments, efficacy tests are not recommended, because the study is not designed to detect differences between types of surgery, therefore, for clinical outcomes the analyses will focus mainly on descriptive analyses using mean (standard deviation) or median (interquartile range) for continuous outcomes and absolute frequencies and percentages for categorical outcomes. For the specific objective of the degree of variability of the bleeding methods, the coefficient of variation of each method within the surgical techniques will be calculated. The STATA software version 14.0 ® will be used.					
Key Words	Placenta accreta spectrum, Hysterectomy, resective reconstructive treatment.					

Amendment	1.0			
Rationale				
Table of Contents	Included			
Synopsis	Included			
6.3 Specific objectives	Objective 1 is deleted: To evaluate the willingness of the team of gynecologists to recruit patients for a clinical experiment. This is eliminated because it would be 100% because the team of intensivist gynecologists of the placental accreta spectrum clinic have signed the log of responsibilities. Compliance with this agreement is difficult to measure because women who might be eligible are not known and were not identified by gynecologists. Objective 4 is deleted: To measure the frequency and describe the cross-over ratios in each group using random assignment of the intervention. This is eliminated because there is only one cross-over ratio. This ratio is described in section 9.4 Study groups of the protocol. Objective 5 is modified: The purpose of this objective is clarified, which is to measure how concordant the methods for measuring bleeding are. The secondary clinical outcomes or complications are by clinical diagnosis and there is no doubt about them. Objective 6 is deleted: To identify the administrative barriers to the performance of the randomly assigned procedure is eliminated because in this study there are no administrative withdrawals. Objective 7 is deleted: To evaluate the comparability and generalizability of the sample of patients studied is eliminated because in this type of study the patients are highly selected, with very strict criteria. Therefore, the comparability and generalizability is very low.			

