6.1.Primary objective: To evaluate the feasibility of the parallel experimental design, the willingness to participate of eligible patients, and the outcome measures for conducting a randomized phase III clinical experiment comparing partial myometrial resection with hysterectomy in patients with PAS, carried out in 3 different centers, including Fundación Valle del Lili, in a period of 24 months.

6.2.Specific objectives:

- 1. To measure the proportion of eligible patients who agree to participate in this comparison.
- 2. To measure the percentage of screening failure.
- 3. To describe the confirmation of the presence or absence of placental accretenotic spectrum in each case.
- 4. To identify the degree of variability between the different methods of measuring intraoperative bleeding in each of the techniques.

6.3.Secondary objectives:

- 1. Clinical and sociodemographic characterization of the patient.
- 2. To identify the characteristics of the patient's current pregnancy.
- 3. To describe the clinical outcomes of interest in patients randomized to hysterectomy or partial myometrial resection.
- 4. To categorize the severity of surgical complications according to the Clavien Dindo classification.

7. Hypothesis

7.1.Primary hypothesis: It is possible to recruit, randomize, operate and follow-up patients recruited for an experiment comparing two surgical techniques in PAS (Hysterectomy Vs Partial myometrial resection) in a period of 24 months or less.

8. Outcomes measures/endpoints:

8.1.Primary endpoints:

- Proportion of eligible patients who agree to participate in the study.
- Screening failure percentage
- Percentage of patients assigned to each arm of the study.
- Percentage of patients with crossover between assigned study arms.
- Number of subjects who complete follow-up at 42 days postpartum.

8.2. Secondary endpoints:

- Maternal death
- Intra-surgical bleeding volume measured in mL.
- Blood component transfusion requirement, median transfusion of red blood cell units (RBCU)
- Compliance with at least one WHO Near Miss criterion (See Appendix 1)
- Ureteral injuries.
- Bladder injuries
- Need for surgical reoperation.
- Admission to the Intensive Care Unit.
- Days of post-operative hospital stay.
- Use of uterine tamponade with hydrostatic balloons.
- Presence of supra fascial hematoma
- Presence of postoperative ileus
- Vital status of the newborn
- Weight of the newborn

9. Methods:

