Use of vascular interventions	What type of vascular intervention was used during the surgical management of PAS	Qualitative nominal	 1.None Ligation of internal iliac arteries Endovascular occlusion of the internal or common iliac arteries (balloons) Clamping or ligation of the aorta Aortic endovascular occlusion (Balloon) Manual compression of the aorta 	Frequency and percentages
Use of cell saver	Cell saver was used during the surgical management of PAS	Qualitative nominal	0.NO 1. YES	Frequency and percentages
start surgery hour	Start surgery hour	NA	Hours and minutes	
End surgery hour	End surgery hour	NA	Hours and minutes	
Duration of surgery	Duration of the surgical procedure in min	Qualitative nominal	Number	Tendency and dispersion
Hystological confirmation of PAS	Hystopathology reports a excluyent or confirmative diagnosis of PAS	Qualitative nominal	0. NO 1. YES 2. NON AVAILABLE HYSTOPATHOLOGY	Frequency and percentages

PAS invasión degree	Most high degree	Qualitative	0.	Accreta	Frequency and
related with	of PAS according	nominal	1.	Inccreta	percentages
hystopathology	hystopathology		2.	Percreta	

Clinical outcomes						
Variable	Definition	Tipe of	Operative leve	Outcome		
		variable	-	measure		
Intra-surgical	Total blood loss	Continuous	Number	Tendency and		
bleeding volumen for	during the	quantitative		dispersion		
pads stimation	procedure for pads	1		1		
•	calculation					
Intra-surgical	Total blood loss	Continuous	Number	Tendency and		
bleeding volumen for	during the	quantitative		dispersion		
suction stimation	procedure for	1		1		
	suction calculation					
Intra-surgical	Total blood loss	Continuous	Number	Tendency and		
bleeding volumen for	during the	quantitative		dispersión		
Reolecting bag	procedure for	1		Ĩ		
stimation	recollecting bag					
	calculation					
Intra-surgical	Total blood loss	Continuous	Number	Tendency and		
bleeding volumen	during the	quantitative		dispersion		
	procedure	•		-		
Hospital admission	Hospital admission	NA	Day/month/year	NA		
date	patient date					
Hospital discharge	Hospital discharge	NA	Day/month/year	NA		
date	patient date					
Numbers of day in-	Total numbers of	Continuous	Number	Tendency and		
hospital	day in-hospital	quantitative		dispersion		
Numbers of day of	Total numbers of	Continuous	Number	Tendency and		
postoperative stay at	day of	quantitative		dispersion		
hospital	postoperative stay					
	at hospital					
Admission to intensive	The patient was	Qualitative	0. NO	Frequency and		

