Type of uterine incision			
Upper segment			
Lower segment			
Fundic			
FIGO Classification for PAS			
Grade 1			
Grade 2			
Grade 3 A			
Grade 3B			
Grade 3C			
Topographic classification of			
PAS			
S1 %			
S2%			

Classification according to		
[name]		
Type 1		
Type 2		
Туре 3		
Type 4		
Use of vascular interventions		
Use of cell saver		
Duration of surgery		
PAS confirmation for		
hystopathology		
Ivasion grade of PAS for		
hystopathology		

Tabla 4: Clinical outcomes

	Total, n=60	Group 1: Hysterectomy	Group 2: partial myometrial resection
Total volume of intra-surgical			
bleeding			
Admission to ICU %			
Number of days of ICU stay (Median			
IQR)			
Patient meets Near Miss criteria%			
Blood component transfusion% %			
RBCU transfused (Median RIC)			
FPU transfused (Median RIC)			
CPU transfused (Median RIC)			
Fibrinogen administration %			
Use of hydrostatic plugging with			
balloons %			
Bladder Injury %			
Ureteral Injury %			
Intestinal injury %			
Need for surgical reintervention %			
Arterial thrombosis %			
Post operative ileus %			
Supra fascial hematoma %			
Surgical wound infection %			
Surgical complications according			
Clavin Dindo classification			
Newborn status			
Newborn Weight			

Bleeding	measures	Hysterectomy	Partial myometrial resection
methods			
Intra-surgical	bleeding	%CV	%CV
volumen for pads	stimation		
Intra-surgical	bleeding	%CV	%CV
volumen for suction	on stimation		
Intra-surgical	bleeding	%CV	%CV
volumen for Rec	olecting bag		
stimation			

17. REFERENCIAS:

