Objective measurement of the total intraoperative bleeding volume will be performed by 3 means:

A. Quantification of bleeding present in intraoperative suction devices: The surgical team will make a visible mark on the suction devices at the time of initiation of surgery. The volume that the amniotic fluid will occupy in said devices will be taken into account. To this end, before performing the hysterotomy, the surgeon will notify the anesthesia and nursing team to make an additional mark on the suction device. Similarly, when the baby and all the amniotic fluid have been extracted, the surgeon will again notify the anesthesiology and nursing team, to make a new visible mark on the suction device.

A record will be kept of any volume of sterile solutions used to irrigate the operative field (saline, lactate Ringer). This volume will be subtracted from the final volume count, to avoid overestimating the bleed.

B. Weight quantification of blood-soaked compresses: Cleaning of the operative field with a compress will be preferred and not with suction devices. The blood-soaked compresses will be removed from the operative field and stored in a sterile container in case intraoperative cell recovery is required. At the end of the surgery, the weight of the soaked compresses will be performed and from the value obtained, the "dry weight" will be subtracted from the number of quantified compresses. The surgical team will previously know the weight of each compress used in your institution

C. Quantification of vaginal bleeding with a calibrated collection bag: All participating centers will use a blood collection bag that will be placed under the perineum of the patient before starting the surgery. This bag has a system for

measuring the volume collected that will be quantified at the end of the surgery. The Brass V® brand collection bags will be provided by the executing institution and sent to the participating institutions to ensure the standardization of vaginal bleeding measurement.

At the end of the surgery, an objective estimate of bleeding will be made by adding the volume of bleeding from the suction devices, that of the compresses and that of the vaginal bleeding collection bag.

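### Specific objective 4 asks for variability between bleeding-measurement methods, but its assigned analysis is a per-method %CV across patients, for three components that are summed into one total

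*Combined protocol and SAP*

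**What the plan says.** Specific objective 4 (section 6.2 and the synopsis) reads: "To identify the degree of variability between the different methods of measuring intraoperative bleeding in each of the techniques".

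The analysis for that objective is one sentence, in section 9.14 and in the statistical part of the synopsis: "the coefficient of variation of each method within the surgical techniques will be calculated". The bleeding-methods table in section 16 has rows for pads, suction and collecting bag, a column for each arm, and %CV in every cell. It has no row or column for a difference between methods.

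Appendix 5 (principal investigator roles, item 10) describes the measurements. Suction volume is corrected for amniotic fluid and irrigation, compresses are weighed against their dry weight, and a calibrated bag collects vaginal blood. At the end, "an objective estimate of bleeding will be made by adding the volume of bleeding from the suction devices, that of the compresses"; the bag volume is the third term of this sum. The same item states: "Cleaning of the operative field with a compress will be preferred and not with suction devices". Visual estimation is excluded, and no other measurement of the same volume is described.

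The clinical-outcomes table in section 15 defines the pads, suction and bag variables each as "Total blood loss" by the respective calculation. It lists the overall bleeding volume as a fourth variable. All four have tendency and dispersion as the outcome measure.

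**The concern.** The objective is about a relation between methods. The statistic assigned to it describes one method at a time. Because the three quantities are parts of a sum, not three readings of the same quantity, putting their CVs side by side does not supply the missing comparison.

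If the plan is followed exactly, the report will answer objective 4 with six percentages that do not bear on it. The volume of intraoperative bleeding is the outcome that section 2 proposes as primary for the definitive trial, and Appendix 5 treats its correct measurement as basic to planning that trial. Readers may therefore look to this table for evidence on how well bleeding is measured, and it holds none.

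**Working it through.** The plan gives no CV, variance or expected volume, so there is no figure to reproduce. The check is algebra and illustration.

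**Inputs from the documents.** There are three means of collection, and the total is their sum (Appendix 5). Section 15 has one variable per means per patient. The surgical note in Appendix 11 shows the three values in two places, but Appendix 5 describes only one measurement of each. The CV can therefore only be taken across patients; this is an inference, since 9.14 does not say so.

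**Formula.** For patient *i* and component *k*, write X_ik = T_i × p_ik + e_ik. Here T_i is the patient's true loss, p_ik the share reaching that device, and e_ik the measurement error. The planned statistic is CV_k = SD(X_ik) / mean(X_ik), taken over the patients in one arm. Two limiting cases without error show what it picks up:

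- If every patient has the same split, p_ik = p_k and CV_k = CV(T) for all three components. The table then shows only differences between patients, three times over.
- If every patient has the same loss, CV_k = SD(p_ik) / mean(p_ik). The table then shows only how the blood was split. That depends partly on how the field is cleared, where Appendix 5 states a preference.

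**Second case in numbers (invented volumes, n = 4, sample SD).**

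| Patient | Pads | Suction | Bag | Total (mL) |
|---|---|---|---|---|
| 1 | 700 | 250 | 50 | 1000 |
| 2 | 250 | 700 | 50 | 1000 |
| 3 | 300 | 500 | 200 | 1000 |
| 4 | 800 | 200 | 0 | 1000 |
| Mean | 512.5 | 412.5 | 75 | 1000 |
| SD | 278.0 | 232.3 | 86.6 | 0 |
| CV | 54% | 56% | 115% | 0% |

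For example, pads: 278.0 / 512.5 = 0.542. Bag: 86.6 / 75 = 1.155. The bag has the smallest SD and the largest CV, because its mean is small. No device has any error here.

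**Dependence on pairing within patients (assumed values).** Take 30 patients in one arm (60 at 1:1) and log-normal components with means set at 1000 mL (pads), 800 mL (suction) and 200 mL (bag). The values of each component stay fixed; only the pairing of suction with pads within patients changes.

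| Pairing | CV of each component | Correlation, pads with suction | CV of total |
|---|---|---|---|
| Same order | 38.6% | 1.0 | 38.6% |
| Random | 38.6% | −0.11 | 26.4% |
| Reversed | 38.6% | −0.99 | 8.3% |

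Doubling every suction reading also leaves its CV at 38.6%. The planned table would be identical in all of these situations.

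**What the recorded data can answer.** In the four-patient example the shares of the total are 70, 25, 30 and 80% (pads), 25, 70, 50 and 20% (suction), and 5, 5, 20 and 0% (bag). The medians are 50%, 37.5% and 5%. Medians of shares need not add to 100%.

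**The case against.** The strongest reply has four parts.

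First, a reader might infer that the six CVs are all the plan says about the components, or that the methods are not set beside one another at all. The documents do not support that. Section 15 assigns tendency and dispersion to each component, and 9.14 summarises continuous clinical outcomes by mean (SD) or median (IQR). The table also places relative spread across patients side by side. This stands and limits the point. It does not remove it: no table shell shows the component summaries (Table 4 has only the total), and relative spread of different parts of a sum is not variability between methods.

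Second, 9.14 paraphrases the aim as "For the specific objective of the degree of variability of the bleeding methods", which in a translated text could mean the variability of each method taken alone. But the objective itself says "degree of variability between the different methods of measuring intraoperative bleeding" in the synopsis and in 6.2, so the two wordings need aligning in any case. The Amendment 1 summary describes the aim as concordance; that is a change log, and nothing here rests on it.

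Third, the section 15 labels might suggest that each device estimates the whole loss, so that agreement statistics would be the remedy. Appendix 5 rules this out by adding the three volumes, and the labels may be translation wording. Agreement between summed components has no meaning, so such statistics are not proposed.

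Fourth, the volumes above are invented. The common measuring protocol, standard bag and assigned measurer may make splits more uniform than in the example. That is fair: the example shows what can happen, not what is likely. In the limit of a uniform split, however, the CV reflects differences between patients and still does not compare methods.

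**Conclusion.** The point holds in a limited form. The only analysis assigned to specific objective 4 cannot answer it, because a %CV across patients for one part of a sum mixes differences between patients, the split and measurement error. It gives no comparison within patients, and for summed components such a comparison would not be meaningful.

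The size is minor: one descriptive objective and one table. No primary endpoint depends on it. A reader might infer that planning of the definitive trial is compromised, or that the devices will be declared unreliable. The documents do not support either: the spread of total bleeding is planned separately (8.2, section 15, 9.14, Table 4), and no stopping, progression or sample-size rule uses the %CV.

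The conclusion rests on Appendix 5 being the operative definition of the total, and on the CV being taken across patients. It does not depend on the invented volumes.

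**What to change.** 1. Reword objective 4 in 6.2 and the synopsis to what the data can answer. For example: to describe, in each surgical technique, the volume collected by suction, weighed compresses and vaginal bag, and the share of each in total intraoperative blood loss. State that concordance or reliability of methods is not assessed, because no repeat or independent measurement of the same volume is planned.
2. In 9.14, the synopsis and the bleeding-methods table, replace the %CV with each component's volume (mL) and share of the total (%), as median (IQR) by arm.
3. In section 15, define the pads, suction and bag variables as the blood volume collected by that means, and the overall volume as their sum, in line with Appendix 5.

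This replaces the question with an answerable one; it does not answer the question of concordance. If the sponsor wishes to keep that question, a repeat or independent measurement of the same volume would have to be added, which is a design choice beyond this correction.

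Cost: a protocol amendment submitted to the ethics committee (Appendix 5, study coordinator functions, item 16), covering one objective, one analysis sentence, the matching synopsis text, three or four variable definitions and one table shell. No new data are needed, since all three components and the total are already recorded for each patient.
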